14.6. Secondary analyses

14.6.1. Confounding

Randomization of 18 schools from within Field Centers to each of two study conditions reduces the risk of substantial imbalance on important prognostic factors between the two conditions. Even so, such imbalance is more likely in a group-randomized trial involving only 36 schools than in most randomized clinical trials involving hundreds of participants. Left alone, such imbalance could confound the true relationship between condition and the primary endpoint in the primary analysis. As a result, we propose a series of secondary analyses designed to explore the potential for confounding, and where found, to control for it statistically.

As noted below in the section on preliminary analyses, we propose to examine the baseline data for evidence of imbalance between the two study conditions on factors of potential prognostic significance. Factors that may prove to be potential confounders include race/ethnicity and socio-economic status, for example. Where found, we plan to add those variables to the models used in the primary and secondary analyses to estimate effects computed as though the two study conditions were balanced on those factors.

One important series of secondary analyses explores the potential confounding influence of differential refusals at the 8th grade survey. It is possible that girls in the intervention schools are more likely to refuse to participate in the follow-up survey if they have been relatively inactive. Ignored, this pattern could bias the estimate of the intervention effect away from the null hypothesis. We propose to explore this possibility in several ways. First, we plan to examine the baseline data of girls who are selected at follow-up to compare those who participate and those who refuse to participate at follow-up. If a net difference of more than 10% is observed in the average MET-weighted minutes of MVPA between the two study conditions, we plan to repeat the primary analysis using multiple imputation of missing values due to refusal. The multiple imputation procedure builds on a regression equation that uses school- and individual-level data to predict MET-weighted minutes of MVPA.

14.6.2. Mediation

As noted in section 4, the TAAG design provides 8th grade data from all girls who participated in the 6th grade survey and who are still present in the participating schools. Even though attrition may be as high as 36% over two years, this approach provides a modest sample (likely 25 girls per school) and one that is well suited for exploration of girl-level mediation effects. As a result, we plan to pursue girl-level mediation analyses in those cohort data.

In mediation analyses, potential mediating variables are examined to determine whether they change in response to the intervention and whether they predict subsequent activity change. They are also examined to determine whether they diminish the intervention effect when added to the primary analysis, as substantial diminution is evidence for mediation (Baron, 1986; Judd, 1981). Leading girl-level candidates as mediators in TAAG include self-efficacy, change strategies, enjoyment of physical activity, enjoyment of physical education, perceived benefits and barriers to physical

activity, perceived competence for physical activity, social support, perceived environment and recreational facilities, and school climate for physical activity.

As elaborated in the Appendix to Chapter 14, we plan to calculate propensity scores to predict the likelihood of leaving the original school between 6th and 8th grade. This allows us to repeat the girl-level mediation analyses adjusting for the propensity score to obtain effect estimates computed as though the propensity to leave was the same in the two study conditions.

In addition to girl-level mediation, we will explore school-level mediation. School-level mediators can be either measured independently from measures taken in girls or calculated by taking the mean of girl-level measurements across a school. An example of the former would be a score assigned by an observer to rate the physical activity facilities for a school. An example of the latter would be a mean score calculated for the school based on the rating of those same physical activity facilities by each girl during the school survey. School-level mediators will be examined both in the cohort data and in the serial cross-sectional data, and the methods are parallel to those described above for girl-level mediation. For example, in a cohort analysis, we might enter both the girllevel score rating physical activity facilities and the observer's score rating those same facilities as mediators to gauge whether they explain a portion of the intervention effect on physical activity. In a cross-sectional analysis, we might enter the observer's rating or the average of the girls' ratings to gauge whether they explain a portion of the intervention effect. As noted by Raudenbush & Bryk (2002) environmental- and individual-level mediators often have different coefficients, and so different interpretations, even when they appear to measure the same general construct (e.g., guality of physical activity facilities). Examining both separately and together rather than just either alone is likely to provide a clearer understanding of how the intervention effects are mediated, so long as care is taken in the interpretation of the results.

14.6.3. Effect modification

We propose effect modification (moderation) analyses in the serial cross-sectional data and in the cohort data. In the former, we compute time x school x stratum means in the first stage, and then perform a stratified analysis of covariance on the 8th grade data, adjusting for 6th grade school means. In the latter, we perform a stratified analysis of covariance, but adjust for individual-level MVPA. For each potential moderator, we test for homogeneity of the intervention effect across subgroups of girls defined by the levels of that variable. The effect modifier is added as a main effect and as an interaction with condition in the fixed-effects portion of the model, and as an interaction with school in the random-effects portion of the model; details on these interaction models are in the Appendix to Chapter 14.

We note of course that power for interactions is always less than for main effects, and so examination of effect modification is primarily to help us understand the pattern of findings and not to test *a priori* hypotheses. The variable we consider of most interest as an effect modifier is baseline weight status (below the median, above the median). Other descriptive variables that we consider as potential effect modifiers include demographic characteristics, sports activity participation history, acculturation, whether an adult is home after school, and whether transportation is available after school. A

significant interaction between any of these variables and study condition provides evidence of effect modification.

As elaborated in the Appendix to Chapter 14, we plan to calculate propensity scores to predict the likelihood of leaving the original school between 6th and 8th grade. This allows us to repeat the moderation analyses adjusting for the propensity score to obtain effect estimates computed as though the propensity to leave was the same in the two study conditions.

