14.4. Type I error rate

The Type I error rate is 5% and all tests are two-tailed.

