For immutable factors, such as age or ethnicity, we look at moderation in the main crosssectional design by adapting our primary analysis to include post hoc stratification on the moderator. In the first stage of the analysis, we stratify girls based on a median split on age, using the grade-specific study-wide median for the baseline and follow-up data, respectively; as a result, stratum is crossed with time and school. We then regress the girl's MET-weighted MVPA on school, time (baseline or follow-up), stratum (hi or lo), their interactions, ethnicity and week of data collection; study condition is not included in the model:

$$MVPA = school + time + stratum + ethnicity$$

+time × school + time × stratum + school × stratum (5)

+time \times school \times stratum + week + error

Here, all terms except for week and residual error are modeled as fixed effects. Of interest in this first stage is the estimation of ethnicity-adjusted school means for MVPA, estimated for each school at each combination of time x stratum.

Given c=2 conditions, f=6 Field Centers, s=2 strata, t=2 time points, and g=3 schools per Field Center per condition, we have 144 ethnicity-adjusted time x stratum x school means from the first stage. The 72 follow-up means provide the values for the dependent variable in the second stage, while the 72 baseline means are used as values for the covariate MVPA_{baseline}. The full model for the second stage analysis is: $MVPA = condition + MVPA_{baseline} + fieldcenter$

+condition \times fieldcenter + school(condition \times fieldcenter)

+stratum + stratum × condition + stratum × fieldcenter

+stratum × condition × fieldcenter + stratum × school(condition × fieldcenter)

Condition, baseline MVPA and stratum are fixed effects while Field Center and school are random effects; in this model, there is no residual error beyond school, and we use the term school instead of residual error to avoid confusion.

In a preliminary step, we evaluate several interaction terms, which we expect to be zero. As in the primary analysis, we evaluate the condition x center interaction; in addition, we evaluate the stratum x center and condition x stratum x center interactions. If any of those interactions are significant, we interpret the results based on the full model. However, if those interactions are not significant, we delete those terms from the second-stage analysis and pursue a reduced second-stage model:

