A.4.5.1.2. Moderators that could change over time

There are also moderators that could change over time at the individual level, such as BMI. Evaluation of moderation for such variables is complicated in the main nested crosssectional design because we have different girls at baseline and follow-up. It is not at all clear that a median split of the sample at follow-up necessarily divides the girls in the same way they would have been divided at baseline, even if the same median were used for both samples. Girls change over time on variables like BMI, and some girls who might have been below the median if measured at baseline might be above the median if measured at follow-up. Application of the analysis described above for an immutable moderator would require the assumption that change in BMI over time did not affect the allocation of girls into the strata. It would also require the assumption that the intervention did not affect BMI. If those assumptions are not acceptable, and they likely are not, then it would be better to restrict evaluation of effect modification by such changeable moderators to the cohort analysis, where girls can be stratified according to their baseline level. Power for interactions in those models is improved to the extent that the cohort analysis is stronger, but is harmed to the extent that the cohort sample is appreciably smaller.

A.4.5.2. Post hoc stratification for school-level moderators (e.g., % free and reduced lunch)

It is not possible to stratify girls within a school on a school-level moderator, because all girls in the same school have the same value on that moderator. As a result, stratification for school-level moderators must occur at the second stage; the first stage of this analysis is identical to that proposed for the primary analysis. We regress the girl's MET-weighted MVPA on school, time (baseline or follow-up), their interaction, ethnicity and week of data collection; study condition is not included in that model:

$$MVPA = school + time + time \times school + ethnicity + week + error$$
(9)

Here, all terms are modeled as fixed effects, except for week and residual error. Of interest in this first stage is the estimation of ethnicity-adjusted school means for MVPA, estimated for each school at 6^{th} grade and at 8^{th} grade.

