Given c=2 conditions, f=6 Field Centers, t=2 time points, and 3 schools per Field Center per condition, we have 72 ethnicity-adjusted time x school means from the first stage. The 36 follow-up means provide the values for the dependent variable in the second stage, while the 36 baseline means are used as values for the covariate MVPA_{baseline}. We stratify the schools based on a median split of the baseline school-level % free and reduced lunch, using the study-wide median. Stratification at the school level results in an uneven distribution of schools among the condition x stratum x Field Center cells, with an average of g=1.5 schools per cell, but school remains balanced for all main effects. We then conduct a second-stage analysis on those stratified means. The full model for the second stage analysis is:

 $MVPA = condition + MVPA_{baseline} + fieldcenter + stratum$

+condition \times fieldcenter + condition \times stratum + stratum \times fieldcenter (10)

+stratum × fieldcenter × condition

+school(condition × stratum × fieldcenter)

Condition, baseline MVPA and stratum are fixed effects while Field Center and school are random effects; in this model, there is no residual error beyond school, and we use the term school instead of residual error to avoid confusion.

In a preliminary analysis, we evaluate several interaction terms, which we expect to be zero. As in the primary analysis, we evaluate the condition x center interaction; in addition, we evaluate stratum x center and stratum x center x condition interactions. If any of those interactions are significant, we interpret the results based on the full model. However, if those interactions are not significant, we delete those terms from the second-stage analysis and pursue a reduced second-stage model:

 $MVPA = condition + MVPA_{baseline} + fieldcenter + stratum$ (11)

+condition × stratum + school(condition × stratum × fieldcenter)

The expected mean squares for this model are shown below:

Source	df		E(MS)	MS
Intercept		= 1		
Condition	c-1	= 1	$\sigma_{g:csf}^2 + fsg\sigma_c^2$	MS _c
MVPA _{baseline}		= 1		
FieldCenter	f -1	= 5	$\sigma_{g:csf}^2 + sgc\sigma_f^2$	MS_{f}
Stratum	s – 1	= 1	$\sigma_{g:csf}^2 + gcf\sigma_s^2$	MS _s
Condition × Stratum	(c-1)(s-1)	= 1	$\sigma_{g:csf}^2 + gf\sigma_{cs}^2$	MS _{cs}
School	cfs(g-1) = 12		$\sigma^2_{g:csf}$	MS _{g:csf}
	+(c-1)(f-1) = 5		from condition x field cent	er
	+(s-1)(f-1) = 5		from stratum x field center	

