Under the original plan, we expected to have 49 girls per school available in the cohort if we selected 120 girls per school at baseline given a two-year attrition rate of 36% and annual refusal rates of 20%. That figure is reduced to 25 girls per school given only 60 girls per school at baseline. With 36 schools, that still provides 900 girls in the cohort, and the degrees of freedom for those analyses are unchanged, as they are still based on 36 schools. Power calculations for an intervention effect on a hypothesized mediator indicate that there is 80% power for an effect of 0.21 sd units and 90% power available for an effect of 0.25 sd units. An effect size of 0.25 sd units is widely considered to be small (Cohen, 1988). In contrast, our hypothesized intervention effect on MET-weighted minutes of MVPA of 10% represents an effect size of 14.5/86=0.17 sd units, which is quite small. This is why, the power for the mediation analysis is reasonable even with a reduced baseline sample.

Power for moderation is diminished by reducing the size of the baseline sample, but is already poor, so we don't do too much harm by reducing it further.

A.4.7. Power Calculations for PWC₁₇₀

Cardiovascular fitness will be assessed by the Physical Work Capacity 170 (PWC₁₇₀) cycle ergometer test. For the PWC₁₇₀ test, the outcome measure will be the predicted power output based on a two-stage required to elicit a heart rate of 170 beats/min. We will express, PWC₁₇₀ as kilogram-meters per minute per kilogram lean body weight (kg-m/min/kg). The estimates used in the power calculations below were from studies that controlled for total weight, rather than more precise measures of lean body weight that we will use. Therefore, the estimates shown here may be conservative.

Using a cross-sectional design, we will model the 36 school-level fitness means at the end of 8th grade as a function of treatment condition, site, and school. Power calculations were performed for a 2-sided type I error rate of 0.05. We assumed a mean and standard deviation for PWC₁₇₀ of 11 ± 2.7, an ICC estimate of 0.01. The following table shows the power to detect a 5% or 6% difference in fitness at 8th grade as a function of the number of girls invited to participate in the fitness measure in each school, with the expectation that 80% will participate.

POWER FOR PWC ₁₇₀ - 36 Schools				
Girls Invited	Intervention effect			
Per School	5% 6%			
60	0.88	0.96		
50	0.84	0.94		
40	0.78	0.91		
30	0.68	0.83		

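### Exploratory effect-modification tests cut continuous moderators at the median, which costs power if modification is graded, in tests already poorly powered

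*Protocol*

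**What the plan says.** Section 14.6.3 sets the form of the test: for each potential moderator, "we test for homogeneity of the intervention effect across subgroups of girls defined by the levels of that variable". It names the lead moderator and its cut: "The variable we consider of most interest as an effect modifier is baseline weight status (below the median, above the median". The Appendix carries this through in its worked models:

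- **Girl level, A.4.5.1.1:** "we stratify girls based on a median split on age". The stratum × condition interaction is then tested on 1 and 33 df.
- **School level, A.4.5.2:** "We stratify the schools based on a median split of the baseline school-level % free and reduced lunch, using the study-wide median". The interaction is tested on 1 and 26 df.
- **Changeable moderators such as BMI, A.4.5.1.2:** these go to the cohort analysis, "where girls can be stratified according to their baseline level".

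The protocol is candid about status and strength. Section 14.6.3 says effect modification is examined "primarily to help us understand the pattern of findings and not to test" a priori hypotheses. A.4.6.2 says: "Power for moderation is diminished by reducing the size of the baseline sample, but is already poor". At 120 girls invited and ICC 0.010, 0.003 and 0.000, Appendix Table 1 (girl level) prints 34%, 48% and 59%, and Table 2 (school level) prints 18%, 26% and 32%. On error rate, section 14.4 says: "The Type I error rate is 5% and all tests are two-tailed".

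**The concern.** BMI, age and % free/reduced lunch are recorded on continuous scales (sections 9.3.2, 9.5.7 and 9.6.1). The protocol gives no reason to expect the effect to change at the study-wide median. Cutting there treats a girl just above the median like the heaviest girl and unlike one just below it. If the gradient is smooth, that discards information that has already been collected and paid for.

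The protocol writes out the models, expected mean squares and power for the split, so this is a stated choice and not a detail left open. What is at stake is the chance of seeing real modification by weight, age or school poverty, and the precision with which its pattern is described. No primary or secondary aim depends on it.

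**Working it through.** **Inputs from the protocol.** Mean 156.4 and SD 94.9 MET-minutes, 18 schools per condition, 20% refusal so 120 × 0.8 = 96 girls measured, and ICC 0.010, 0.003 or 0.000 (section 14.5.4, Table 14.1). Interaction 6.67% of the mean, variances reduced by 10%, 33 and 26 error df (A.4.5).

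**Assumption on dose.** Of the girls measured, 80% have full and 20% partial dose: 0.8 × 15.6 + 0.2 × 9.4 = 14.36, and 14.36/15.6 = 0.92. With this mix, two-sided noncentral-t power for the primary analysis is 86.7%, 96.6% and 99.0%, against 87%, 97% and 99% in Table 14.2. The interaction to detect is 0.0667 × 156.4 × 0.92 = 9.60 MET-minutes.

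**Plan's figures, school level.** Variance = 4 × 0.9 × 94.9² × (ICC + (1 − ICC)/96)/9. At ICC 0.003 the SE is 6.94, the noncentrality 9.60/6.94 = 1.38 and power 26.6%. Over the three ICCs this gives 19%, 27% and 33%, within one point of Table 2.

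**Plan's figures, girl level.** Variance = 4 × 0.9 × 94.9² × (ICC + (1 − ICC)/m)/18, where m is girls per school per stratum. A.4.5 says the number of girls per cell halves, so m = 48; power is then 24%, 30% and 33%. Table 1's 34%, 48% and 59% are approached only with m = 96 (33.8%, 47.6%, 57.6%). I use 48.

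**Information kept by the split.** This is the squared correlation between a moderator and its above-median indicator: 2/π = 0.64 for a normal moderator and 0.75 for a uniform one, so 36% or 25% is lost. For a continuous test with the same upper-minus-lower contrast, I multiply the sampling variance by that factor. At school level this is the whole variance of the school mean. At girl level it is only the (1 − ICC)/m part, because school-to-school variation in slope is not reduced. For girl-level age the continuous test is charged 27 error df, a conservative figure.

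| Moderator | Split (ICC 0.010 / 0.003 / 0.000) | Continuous, uniform | Continuous, normal |
|---|---|---|---|
| % free/reduced lunch | 19 / 27 / 33% | 24 / 34 / 41% | 27 / 39 / 47% |
| Age, m = 48 | 24 / 30 / 33% | 28 / 36 / 42% | 30 / 40 / 47% |

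Example for age at ICC 0.003, normal moderator: 0.003 + 0.637 × 0.997/48 = 0.0162; SE = √(4 × 0.9 × 94.9² × 0.0162/18) = 5.4; noncentrality 9.60/5.4 = 1.78; power 40%.

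**BMI in the cohort.** About 25 girls per school gives m = 12.5, with the other inputs unchanged for comparability. Without baseline-MVPA adjustment, split power of 11–12% becomes 13–16%. If that covariate is assumed to explain half the variance, 18–20% becomes 22–28%. The gain is about 2–9 points.

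**Simulation.** With a normal moderator and linear modification, school-level power was 17%, 24% and 30% (split) against 25%, 35% and 43% (continuous); with a uniform moderator, 17%, 26% and 30% against 23%, 32% and 38%. Girl-level power with a normal moderator was 24%, 30% and 34% against 29%, 41% and 47%. When the true modification was a step at the median, the split did better: 17% against 13%.

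**The case against.** The strongest reply is that little hangs on these tests. Section 14.6.3 disclaims a priori hypothesis testing, section 9.5 warns that power may be inadequate for some moderators, and A.4.6.2 calls it poor. A reader might infer that these analyses decide whether the trial can claim different effects in subgroups, or that a null result will be read as homogeneity; the protocol says neither. This part of the objection stands and limits the weight of the point.

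Second, the larger gains do not belong to the moderator the plan cares most about. It is tempting to apply the 11–12 point gain at ICC 0.003 to weight status. That gain is the normal-moderator case for % free/reduced lunch and age, which are worked examples in the Appendix. BMI belongs in the small cohort and gains far less. This also stands.

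Third, A.4.5 defines effect modification as the upper-half effect minus the lower-half effect, which is directly reportable, whereas a slope needs a linearity assumption. That is a reason to keep the contrast as a display. It is not a reason to make it the only test, since the protocol nowhere posits a step at the median.

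Last, one might scale up Table 1's printed 34%, 48% and 59%. Those figures match only if each stratum holds all 96 girls, contrary to A.4.5's own statement, so they are not a sound starting point. That mismatch needs its own correction.

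**Conclusion.** The point holds as an inexpensive gain in efficiency for exploratory analyses. It is not an error or contradiction in the plan. Under graded modification the median split loses 25–36% of the sampling information. Avoiding it is worth about 5–15 power points for % free/reduced lunch (27% to 34–39% at ICC 0.003), 4–14 for age (30% to 36–40%) and 2–9 for BMI in the cohort.

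The ranges rest on the assumed 80/20 dose mix, a moderator between uniform and normal in shape, an approximately linear gradient, 48 girls per stratum for age and, for the top of the BMI range, the assumed baseline adjustment. Power stays below 50% throughout, so the change does not turn these into confirmatory tests. Moderators that are already categorical are unaffected.

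**What to change.** Make the continuous moderator × condition interaction the test of effect modification in section 14.6.3 and A.4.5:

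- **Girl level, cross-sectional:** in Eq. 5, replace the stratum terms with the grade-centered moderator and its interactions with school and time, giving one slope per school and time. In the second stage, regress the 36 follow-up slopes on condition, baseline slope and Field Center.
- **School level:** in Eq. 11, replace stratum with baseline % free/reduced lunch as a continuous covariate, and test its interaction with condition.
- **Cohort:** use continuous baseline BMI × condition with a random school slope.

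Check linearity as A.4.2.3 already does for covariates, and keep the upper and lower median-split effects as a descriptive display. Restate Tables 1 and 2 on this basis, and reconcile Table 1's girls per stratum as a separate correction.

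The cost is revised wording, recalculated tables and a little more analysis, with no new data and no change to the primary analysis. The downside is reliance on an approximately linear gradient and some loss of power if the modification really is a step at the median; the retained display would help to show that case.
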